8.0 PRE-TREATMENT EVALUATION

Groups 1 and 2, will have a baseline clinical evaluation 3-10 weeks after permanent implant exchange, both by the radiation oncologist and by the plastic surgeon. For Group 1, baseline evaluations will take place shortly before or during IMRT (but the baseline MRI must be completed prior to the start of IMRT). For Group 2, MRI and baseline evaluations will take place approximately 6-8 months after completion of IMRT. The baseline procedures include:

- History and physical exam by a radiation oncologist and a plastic surgeon, including clinical evaluation for implant failure, revisional surgeries, capsular contracture and cosmesis
- Breast-Q® questionnaire
- MRI of the breast (strongly recommended, but not required)
- CBC (Complete Blood Count)
- FACT-B and FACIT questionnaires (only Groups 2A and 2B)

However, at the discretion of the plastic surgeon, the baseline clinical evaluation by plastic surgeon may occur at any time point between the exchange surgery and 10 weeks post-surgery.

The research team will collect baseline demographic data that may relate to possible variability in the study population. Data to be collected includes details on chemotherapy, hormone therapy and surgery.

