The time interval at which follow-up assessments will occur after the intervention (IMRT) will depend on the sequencing of the expander/implant exchange with radiation. Two groups of patients will be evaluated. Group 1 will consist of patients who receive IMRT to the permanent implant and are followed up at 12 ± 2 months and 24 ± 2 months after IMRT. Group 2 will include patients who receive IMRT to the temporary expander and are followed up at $12-18 \pm 2$ months and 30 ± 2 months after IMRT. This sequencing will be determined prior to study enrollment based on whether the patient received neoadjuvant or adjuvant chemotherapy (see Section 3.0 for further details).

Evaluation for implant failure may occur at any time interval between the completion of IMRT to the end of the study period (24 ± 2 months for Group 1 or 30 ± 2 months for Group 2, after IMRT). Capsular contracture and cosmesis will be assessed at baseline, 12 ± 2 months and 24 ± 2 months for Group 1 or $12-18 \pm 2$ months and 30 ± 2 months for Group 2, both following IMRT. The patient will be evaluated for capsular contracture by physical exam and an optional breast MRI, and for cosmesis by Breast-Q[®] questionnaires at these time points. A subset of 10 patients evaluated with cardiac PET scans for exploratory objective #1 will obtain these studies at the time of the RT simulation session and $12-18$ months (± 6 months) after the completion of IMRT. A separate subset of 20 patients to be evaluated for exploratory objectives #2 and #3 will complete the study questionnaires and undergo speckle tracking strain echocardiography, ultrasound of the brachial artery, CPET, and cardiac biomarker measurement at baseline and at the post-treatment intervals specified in Section 10.

Target accrual for this study is 130 patients, to be achieved in 3-4 years of accrual.

Schema

¹**Group 1:** Physical examination by MD, optional Breast MRI, Breast-Q[®] at baseline (after permanent implant exchange, physical exam and Breast-Q[®] may be done after the initiation of IMRT), 12 ± 2 months and 24 ± 2 months post-IMRT. Total length of the follow-up time will be 24 ± 2 months post-IMRT.

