4.2.2 Multi-beam IMRT

Multi-beam IMRT will be performed approximately one month (but no sooner than 2 weeks) after exchange in Group 1. Multi-beam IMRT will be performed at least 4 weeks after mastectomy in Group 2, although it may be performed sooner if the patient has recovered from surgery and the treating physician deems it safe to proceed with treatment. The target volume for IMRT will be contoured according to guidelines specified in Appendix 2. All patients will receive 50-50.4 Gy in 25-28 fractions, which is the standard dose and fractionation for breast IMRT in our department. Prior to each daily treatment, the reproducibility of the patient's position will be verified by kilovoltage (kV) x-rays or Align RT®, an FDA-approved in-room video-based localization system.

A subset of 10 left-sided patients will receive $^{13}\text{N-NH}_3$ PET scans within the radiation simulation session. A CT for coronary calcium scoring and a low-dose CT for attenuation correction will also be obtained at this time. Myocardial blood flow will be measured during rest and at peak stress with $^{13}\text{N-NH}_3$ as a perfusion tracer. A follow-up $^{13}\text{N-NH}_3$ PET study with low-dose CT for attenuation correction will be obtained 12-18 months (\pm 6 months) post-IMRT.

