10.2.2 Group 2B (Mastectomy and no RT participating in sub-study)

4-8 weeks post-surgery:

- Follow-up strain echocardiogram
- CPET
- Flow-mediated dilatation (FMD)
- cardiac biomarkers for assessment of early cardiotoxicity

- FACT-B (Appendix 6) and FACIT-fatigue (Appendix 7) questionnaires for assessment of QOL and fatigue

15-20 weeks post-surgery:

- Follow-up strain echocardiogram
- CPET
- Flow-mediated dilatation (FMD)
- cardiac biomarkers for assessment of early cardiotoxicity
- FACT-B (Appendix 6) and FACIT-fatigue (Appendix 7) questionnaires for assessment of QOL and fatigue

Group 1: IMRT to Permanent Implant

Protocol Activity	Screening		Treatment		Post-Treatment Follow-Up After IMRT completion		
	0-4 weeks	3-10 weeks	Day 1 _f	2-4 weeks	12 months	12-18 months	24 months
Study Week(s)/ Months	0-4 weeks	3-10 weeks	Day 1 _f	2-4 weeks	12 months	12-18 months	24 months
Visit Window	before IMRT	after exchange surgery _e	during IMRT	during IMRT	± 2mo	± 6 mo	± 2mo
Evaluation by Radiation Oncologist _a		X			X		X
Evaluation by Plastic Surgeon _a		X _b			X _c		X _c
MRI at the MSKCC main campus _d		X			X		X
BreastQ Questionnaire		X			X		X
CBC	X			X			
IMRT			X	X			
Pregnancy Test ^h	X						
¹³ N-NH ₃ PET/CT _g		X				X	

- a) Evaluation includes assessment of capsular contracture and cosmesis
- b) May occur at any time point between the exchange surgery and 10 weeks after exchange surgery.
- c) Follow-up clinical evaluations by the plastic surgeon can be from the completion of IMRT or the date of exchange surgery. This will ensure that patients are seen routinely as per standard care and will ease the schedule to accommodate changes in scheduled appointments.
- d) The MRI is an optional assessment but highly recommended
- e) This may be before IMRT or just after the start of IMRT
- f) Patients will be fully registered prior to start of Radiation Treatment (refer to section 15.0)
- g) ¹³N-NH₃ PET/CT for subset of 10 patients who agreed to participate. Baseline occurs during radiation simulation. Follow-up scan occurs 12-18 months (± 6 months) after the completion of IMRT.
- h) Pregnancy Test: Serum pregnancy is required 14 days prior to RT. A urine pregnancy test is also accepted (if performed, must be done at set-up)..

Group 2 and Group 2A: IMRT to Tissue Expander (and participating in sub-study)

Protocol Activity	Screening	Treatment		End of Treatment/ Withdrawal	Post-Treatment Follow-Up After IMRT completion			

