11.0 TOXICITIES/SIDE EFFECTS

11.1 IMRT

Potential acute side effects of IMRT are identical to those associated with radiation delivered with conventional 3D techniques. These include mild-moderate erythema, hyperpigmentation, moist desquamation of the chest wall, fatigue, radiation pneumonitis, predisposition for developing a chestwall skin infection, and/or changes in blood count (<3 and will be scored according to the Common Terminology Criteria for Adverse Events (CTCAE) Version 4.0). Additionally, CBC will be measured at specified time points as per standard care. For pre-menopausal women, the first CBC may be consolidated with the pre-study pregnancy test.

Capsular contracture and cosmesis will be graded by the Baker scoring system and Breast-Q[®] questionnaires at time points specified for Group 1 and Group 2.

At any time following completion of radiation, implant failure can be assessed by surgical intervention requiring implant removal or replacement.

Lactating and pregnant women will be excluded because of potential teratogenic effects of radiotherapy that may be harmful to the developing fetus or nursing infant.

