14.1.2 Capsular Contracture

For the secondary objectives, the incidence of moderate and severe capsular contracture will be examined using proportions of patients who developed Baker grade <II and \geq II capsular contracture, respectively, at 12 or 18 months and 24 or 30 months after IMRT was administered. Incidence of minor revisional surgeries by plastic surgeon will be evaluated by proportions too. Again, the rates (proportions) will be compared across the two groups.

To evaluate cosmesis, the Breast-Q[®] will be utilized in these assessments and will be presented descriptively, giving summary statistics for changes in the Breast-Q[®] scores over time.

Post-treatment MRI outcome is defined as a continuous variable. We will examine the correlation between the 12-month MRI and 12-month Baker score (<II vs \geq II in Group 1 and between the 18-month MRI and 18-month Baker's score in Group 2. The correlation will be assessed by Wilcoxon rank sum tests. We will also examine the sensitivity and specificity of MRI by using Baker score as the gold standard. All patients enrolled will be used for the analysis of secondary objectives if they provided eligible measurements. Analyses for secondary objectives will be done separately for the two groups.

14.1.3 $^{13}\text{N-NH}_3$ PET/CT Feasibility Endpoint

We will assess the feasibility of performing $^{13}\text{N-NH}_3$ PET studies in breast cancer patients undergoing IMRT within the RT simulation session. This involves delivering the dose on time (taking into account the short half life of $^{13}\text{N-NH}_3$), performing all scans successfully, and most importantly, having the patient tolerate all imaging sessions while in the treatment position.

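### Group 1's baseline Breast-Q may be completed during IMRT, the sections on its timing disagree, and an on-treatment baseline can understate later decline in patient-rated cosmesis

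*Combined protocol and SAP*

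**What the plan says.** Three places in the protocol set the timing of the Group 1 baseline questionnaire and examination, and they differ.

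- Section 8.0 gives a window: "Groups 1 and 2, will have a baseline clinical evaluation 3-10 weeks after permanent implant exchange". It then adds: "For Group 1, baseline evaluations will take place shortly before or during IMRT (but the baseline MRI must be completed prior to the start of" treatment).
- The schema note for Group 1 in Section 1.0 says the "physical exam and Breast-Q[®] may be done after the initiation of IMRT", with no limit on how long after.
- Footnote e of the Group 1 schedule table in Section 10, attached to the 3-10 week visit window, says: "This may be before IMRT or just after the start of IMRT".

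On treatment timing, Section 4.2.2 says "Multi-beam IMRT will be performed approximately one month (but no sooner than 2 weeks) after exchange in Group 1". Section 9.2 gives a course of roughly 5-6 weeks.

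On use of the baseline, Section 14.1.2 presents the Breast-Q descriptively, "giving summary statistics for changes in the Breast-Q[®] scores over time". Section 9.3.2 gives a 2-week recall for psychosocial well-being, physical well-being and satisfaction with breasts, and no recall period for satisfaction with outcome. Section 9.3.1 says in general terms that follow-up contracture assessments are compared with baseline.

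**The concern.** A change score needs a starting value that the treatment has not yet altered. Section 8.0 secures this for the MRI but not for the Breast-Q. Section 11.1 lists the possible acute effects of IMRT: "These include mild-moderate erythema, hyperpigmentation, moist desquamation of the chest wall, fatigue", among others. A patient who fills in the Breast-Q mid-course is asked about a fortnight spent on treatment. If those effects lower her score, later recovery from them counts as improvement and offsets any long-term loss.

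The error would flatter the result. Section 3.1 hypothesises that multi-beam IMRT improves cosmesis, and the study has no randomised comparator in which a shared baseline effect could cancel. Nothing in Section 14.1.2 separates baselines taken before IMRT from those taken during it, so the two kinds would be pooled unmarked.

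**Working it through.** The plan states no figure for this point, so there is none to reproduce. The check has four parts.

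**1. How much of the window lies inside the course.** Inputs: window from week 3 to week 10 after exchange, 7 weeks wide (Section 8.0); IMRT start *s* of about one month, earliest 2 weeks, no latest limit stated (Section 4.2.2); duration *d* of 5-6 weeks (Section 9.2). Overlap = min(10, *s* + *d*) − max(3, *s*); share = overlap / 7.

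| Start *s* (weeks after exchange) | Before IMRT (weeks) | Inside IMRT (weeks) | After IMRT (weeks) | Share inside |
|---|---|---|---|---|
| 2 | 0 | 4-5 | 2-3 | 57-71% |
| 4 | 1 | 5-6 | 0-1 | 71-86% |
| 4.34 (30.4 days / 7) | 1.34 | 5-5.66 | 0-0.66 | 71-81% |
| 6 | 3 | 4 | 0 | 57% |
| 6.5 | 3.5 | 3.5 | 0 | 50% |
| 7 | 4 | 3 | 0 | 43% |

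At *s* = 4 and *d* = 5, for example: min(10, 9) − max(3, 4) = 5 weeks, and 5/7 = 71%. Most of the window is inside the course for any start from week 2 up to just under week 6.5.

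**2. What the recall period covers.** For a questionnaire completed *t* weeks after the first fraction, the share of a 2-week recall spent on treatment is min(*t*, 2)/2. It is 50% at *t* = 1 and 100% from *t* = 2 onward. Under footnote e (*t* small) exposure is limited. Under Sections 1.0 and 8.0 it can be complete.

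**3. Effect on mean change.** Let *f* be the share of Group 1 baselines affected and *a* the acute drop in score. The observed baseline mean is the undisturbed mean minus *f* × *a*, so observed change = true change + *f* × *a*. Neither quantity is in the documents. Assumed range:

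- low: 0.25 × 2 = 0.5 points
- middle: 0.50 × 5 = 2.5 points
- high: 0.75 × 10 = 7.5 points

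**4. Room for a pre-IMRT baseline.** Keeping the 3-week lower bound, a start at 4 to 4.34 weeks leaves 1.0 to 1.34 of 7 weeks (14-19%). A start at week 2 leaves none. A pre-IMRT rule therefore requires that lower bound to be relaxed.

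**The case against.** Assessment during IMRT is permitted, not required, and Section 8.0 names the period shortly before IMRT first. If footnote e governs, only the first part of the course is exposed. A reader might infer from the overlap that most Group 1 patients would have an on-treatment baseline. The documents do not support that: a share of calendar weeks is not a share of patients, and nothing says when within the window patients attend. This stands in full.

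The size and even the direction are inferred. Section 11.1 lists potential effects; it does not say when they appear or that they lower Breast-Q scores. Recovery from exchange surgery also acts on this baseline. This stands too, which is why the points above are labelled as assumptions.

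A reader might extend the point to capsular contracture. Section 14.1.2 reports Baker grade as proportions at fixed follow-up times and relates MRI to the Baker score at the same visit. Neither uses baseline; only the general sentence in Section 9.3.1 does. The plastic surgeon's baseline grade is also allowed from the day of exchange, so a pre-IMRT grade may already exist.

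Finally, cosmesis is a descriptive secondary objective with no test or decision rule, and absolute scores at 12 and 24 months are unaffected. That limits the stakes, but a mean change distorted by its baseline stays distorted when reported descriptively.

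**Conclusion.** The point holds for the Group 1 Breast-Q. Sections 1.0 and 8.0 and footnote e disagree on how far into IMRT the baseline may be taken. The wider wording allows a baseline whose recall period lies wholly on treatment, and at the stated timing 71-86% of the window is inside the course. Change in cosmesis could then look better than it is. The size cannot be derived from the documents: 0.5-7.5 points rests on assumed shares of 25-75% and assumed drops of 2-10 points, and its sign rests on acute effects lowering the score.

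The effect on Baker grade is minor. Implant failure and the baseline MRI are unaffected. A reader might also expect an earlier Group 1 baseline to put the two groups' change scores on the same footing. It would not, because Group 2's baseline follows IMRT by design. This is an inexpensive improvement to a secondary analysis; it does not threaten the trial's main conclusion.

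**What to change.** Align the schema note in Section 1.0, Section 8.0 and footnote e so that the Group 1 baseline Breast-Q is completed after exchange and before the first fraction, as the MRI already must be. It should be as close to the start of IMRT as practical, for example at simulation. The 3-10 week entry for the Breast-Q in the Section 16.1 data-form table needs the same edit. IMRT timing need not change.

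Record the exchange date, the assessment date and the number of fractions delivered by then. Keep any baseline taken after the first fraction, but flag it. In Section 14.1.2, give the Group 1 change summary for pre-IMRT baselines, with all baselines as a sensitivity summary.

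The cost is small. Patients are already evaluated by the radiation oncology team before simulation (Section 9.1), and the questionnaire takes about 10 minutes (Section 9.3.2). There are two downsides. Relaxing the 3-week lower bound when IMRT starts early means some recall periods will cover surgical recovery, which may itself lower the score; the recorded dates make this visible. A few patients may also leave the main change summary, which matters somewhat in a group whose guaranteed minimum for the primary analysis is 34 (Section 14.1.1).

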9.0 TREATMENT/INTERVENTION PLAN

9.1 Multi-Beam IMRT-Simulation

Multi-beam IMRT will be performed in the Department of Radiation Oncology on an outpatient basis. Patients will be evaluated by the radiation oncology team and then undergo CT simulation (with contrast is strongly recommended for all patients, but only required for patients enrolled in the optional $^{13}\text{N-NH}_3$ cardiac PET scan subset) for IMRT. At the time of simulation, the patients will be positioned in an immobilization device and undergo a CT scan (slice spacing 2 mm), scanning from C4/5 to the inferior border of the wired breast field, capturing the entire lungs. The isocenter will be placed on a slice at the midpoint between C4-C5 and the inferior border of the breast field. Anteriorly and posteriorly, the point should be placed into the chest wall.

A subset of 10 patients with left-sided breast cancer will undergo a CT for radiation treatment (RT) planning (standard for patients receiving radiation), as well as an $^{13}\text{N-NH}_3$ PET myocardial perfusion scan at the time of the RT simulation session. The rest/stress PET procedure will be performed as follows: A low-dose CT (~40 mA) will be acquired over one PET field-of-view (FOV) centered over the heart, which will be used for attenuation correction of the subsequent PET images. ECG-gated dynamic $^{13}\text{N-NH}_3$ PET studies at rest and during stress will follow immediately. First, the resting dynamic PET acquisition will commence simultaneously with intravenous injection of ~8 mCi of $^{13}\text{N-NH}_3$. PET images will be acquired in 3D dynamic mode for a total of 10-15 minutes. Approximately five minutes after the completion of the resting study, the patient will receive a bolus intravenous injection of regadenoson 0.4 mg over ~20 seconds for the vasodilator stress procedure. Approximately 2 minutes after injection of regadenoson, the stress dose of $^{13}\text{N-NH}_3$ (~12 mCi) will be injected intravenously and dynamic PET imaging will commence simultaneously for a total of 10-15 minutes. An ECG-gated CT scan for calcium scoring assessment will be performed immediately before or after the PET study.

9.2 Treatment and Set-up

Treatment will be delivered over approximately 5-6 weeks in 25-28 fractions, utilizing 6 MV photons. A daily bolus will be applied over the chest wall. The number of gantry angles used for the multi-beam IMRT plan will be optimized for each patient but will generally range between 6-12 beams. The

radiation oncologist will delineate the PTV (planning target volume), according to guidelines specified in Appendix 3.

Two techniques are currently available in the Department of Radiation Oncology and will be employed to verify setup accuracy prior to each treatment:

1) AlignRT employs three ceiling-mounted stereostopic camera units to produce high-resolution and accurate 3D surface image referenced to the treatment isocenter. At each treatment fraction, the system images the current patient position instantaneously. State-of-the-art surface-matching software registers these data to the reference surface within seconds. Couch shifts are displayed to show discrepancies between existing and ideal treatment positions. New coordinates for the optimal couch position are then displayed and may be applied. This system has been FDA-approved. Further information regarding this approval is available on the website:

http://www.visionrt.com/site_files/AlignRT%20SE%20FDA%20Clearance%20Letter.pdf

A 2-step setup procedure has been established to minimize breast tissue deformation. First, the patient's arm and chin will be aligned to match simulation position with real-time AlignRT guidance, to minimize difference in muscle stretching. Then the patient's chest wall surface (including the ipsilateral reconstructed breast and 1/3 of contralateral breast) will be used as the region of interest for alignment.

2) An orthogonal pair of KV images allows optimal visualization of bony anatomy as well as clips in the axilla or the port in a tissue expander. One Trilogy, two 2100EX linear accelerators, and two True Beam linear accelerators with on-board KV imagers are available in the department. Bony landmarks, such as anterior ribs, should be used for alignment at the setup.

9.2.1 Treatment interruptions

In the event that a patient must miss a scheduled treatment for non-toxicity related reasons (ie: weather, sickness, family emergencies, etc) the treatment visit will be made up at the end. If the patient misses more than 5 consecutive treatments, they will be removed from the protocol and considered inevaluable.

9.3 Assessment of Secondary Objectives

9.3.1 Capsular Contracture

Two methods will be employed to assess capsular contracture. These include the current standard assessment tool, the Modified Baker score, and MRI. All follow-up assessments will be compared to the baseline assessments. For all patients, the radiation oncologist should perform the baseline physical evaluation 3-10 weeks after the patient's exchange surgery.

Baker Scoring System (See Appendix 1)

All patients will be assigned a Baker Classification score at baseline and at each follow-up interval by the radiation oncologist and plastic surgeon. The Baker score is a standardized 4-point scale, which integrates the texture and appearance of the breast. Grade I is a normal-appearing, soft breast (a Grade IA breast cannot be detected as an implant, while the implant of a Grade IB breast can be detected by physical examination or inspection); Grade II refers to breast implants that are firm but

appear normal; Grade III includes implants that are firm and appear abnormal; Grade IV capsular contracture is the most severe and includes breasts that are hard, painful, and appear abnormal often with severe distortion [46].

Breast MRI

Longitudinal MR studies will be evaluated for capsular contracture.

